Acute Effect of Melon Manis Terengganu Peel
Powder on Glycemic Response, Satiety, and Food
Intake in Adults at Risk for Type 2 Diabetes

NCT05298111

25 March 2022

Study Protocol

Open-label, randomised, placebo-controlled, crossover study with two intervention arms. The study was conducted in 30 participants and the primary objective is to show an improved glycemic response after Melon Manis Terengganu (MMT) peel powder consumption in people at risk of type 2 diabetes. Besides, the acute effect of MMT peel powder on perceived satiety and energy intake were explored.

Pre-test protocol

Participants were required to obtain adequate sleep (7 to 9 hr) on nights before test days (Hirshkowitz et al., 2015). They were instructed by the researchers to maintain their usual daily food intake and consume a dinner of similar composition and quantity at a similar time before their study visit besides avoiding caffeine consumption such as caffeinated beverages, meals or medications as well as alcohol consumption. This is to minimize within-respondent variability (Al-Mana & Robertson, 2018) as well as ensure similar feelings of satiety and glycemic response on study visits (Kay, 2016). Additionally, participants were required to avoid moderate or strenuous activity (as indicated by the IPAQ-SF) before the test days as this would deplete their glycogen content derived from the liver and muscle. Glycogen can be stored for up to 12 to 48 hr, after which the body switches to oxidative fats and ketones metabolism (Lean, 2015).

To ensure that these habits had not been modified during the study, the participants were instructed to record 24-hr dietary recalls (food logs) and physical activity diaries (IPAQ-SF) as well as take photos of any food and drinks they consumed which were reviewed by the researcher on the test days to ensure accuracy and completeness. Any unclear aspect was clarified on the spot. A copy of the food log was kept by the participants for them to refer back to each study visit to preserve meal accuracy, especially dinner meals consumed before each visit.

They were required to fast for 10 to 12 hr preceding their testing time and hence they were instructed to eat their dinner no later than 10 pm. They were only allowed to consume plain water once their testing period began. The pre-test protocols were no longer in effect once participants finished their testing for the day, and they were free to resume their normal activities and food habits.

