Acute Effect of Melon Manis Terengganu Peel Powder on Glycemic Response, Satiety, and Food Intake in Adults at Risk for Type 2 Diabetes

NCT05298111

25 March 2022

Statistical Analysis Plan (SAP)

Data Checking and Normality Test

Data entry errors and respondent's errors may occur during data entry and answering the questionnaire. Data were checked after they were entered into the SPSS. Data checking was crucial to ensure the accuracy of all the entered data, identify any missing data and any outliers during the data entry. Mistyping responses or entering data was an example of data entry errors in contrast to respondent's errors that happened during answering the questionnaire, for example the participants did not complete the questions or provide an unreadable or illogical response.

Before descriptive statistical analysis was performed, the frequency distribution (histogram) and boxplot were used for checking normality visually. Normally distributed population generated a bell-shaped curve appearance of the histogram with symmetrical about the mean indicates data. Besides, the Shapiro-Wilk test was done for the assessment of normality tests and the data considered to be normal if $p > 0.05$. Hence, according to the findings, the data checkinwas g revealed that all the variables have completed 30 valid frequencies for socio-demographic, anthropometry, biochemical, blood pressure, dietary intake, perceived satiety and physical activity information. Those outputs implied that no missing data value was reported.

Statistical Analysis

The data were analysed by using IBM SPSS system version 21.0 and Nutritionist ProTM software (Version 7.0.0, Axxya Systems).

Descriptive Statistic

A descriptive statistic was used to present all outcomes on socio-demographic information, anthropometric measurement, blood glucose levels, blood pressure measurement, dietary intake, perceived satiety and physical activity. Continuous data were described as mean \pm standard deviation if normally distributed or median (interquartile range) if not normally distributed meanwhile for categorical variables, the data were reported as the number of frequency and percentage. The 2 hr area under the curve (AUC) of blood glucose levels (incremental area above the baseline value) and perceived satiety (hunger, fullness, desire to

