A paired t-test (normally distributed) or Wilcoxon matched pair signed-rank sum test (non-normally distributed) was used to compare the difference of two data between groups (placebo and intervention) on anthropometric measurements, blood glucose levels (iAUC and CMax), blood pressure, dietary intake, physical activity and perceived satiety (AUC). Two-way repeated measures ANCOVA was used to compare the postprandial blood glucose levels between two test products over different time points, controlling for treatment and time to test for treatment by time interaction after adjustment for covariates (age, ethnicity, gender and BMI) (Tongyu & Chong-Do, 2021; J. Wang et al., 2021). Rather than subtracting from baseline data alone, including baseline data as a covariate will improve the analyses' performance. Furthermore, due to random deviations at baseline, the use of baseline subtraction can result in artefactual effects (whether these differences are statistically significant or not) (Blundell et al., 2010). The perceived satiety was analysed using the Friedman non-parametric test. The analysis was considered significant at a p -value ≤ 0.05 . Any significant data was further tested using Wilcoxon matched pair signed-rank sum test.

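### The primary objective of improved glycemic response is tied to no endpoint: iAUC, Cmax and a repeated measures ANCOVA are each tested at 0.05, with no primary test, order, adjustment or success rule

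*SAP*

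**What the plan says.** The protocol (Study Protocol) says that "the primary objective is to show an improved glycemic response" after the peel powder. It describes satiety and energy intake as explored, so it ranks the domains, but it ranks nothing within glucose.

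The SAP (Descriptive Statistic) defines a 2-hour incremental AUC above baseline and a Cmax. Under Bivariate and General Linear Model Analysis both go to a paired t-test or Wilcoxon test, in one list of variables: "anthropometric measurements, blood glucose levels (iAUC and CMax), blood pressure, dietary intake, physical activity and perceived satiety (AUC". The same section continues: "Two-way repeated measures ANCOVA was used to compare the postprandial blood glucose levels", and it gives the purpose as "to test for treatment by time interaction", with age, ethnicity, gender and BMI as covariates. A product main effect is implied by that model but not named as a test. The criterion is general: "The analysis was considered significant at" p ≤ 0.05, with sidedness not stated. The only sequential rule is a Wilcoxon follow-up of significant results, which neither ranks the glucose measures nor adjusts alpha.

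On timing, the SAP (Data Checking and Normality Test) says "Data were checked after they were entered into the SPSS" and reports that "all the variables have completed 30 valid frequencies", with no missing values.

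**The concern.** A reader cannot tell which glucose result answers the primary objective, or which result would count as failure. Three explicit tests, and a fourth that is implied, could each be put forward as the answer after the fact.

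They are not interchangeable. An interaction says that the two curves differ in shape, not that glucose is lower on the product, yet no rule stops a significant interaction from carrying the claim. Separately, iAUC and Cmax can disagree even when the product works, and the plan has no rule for that case.

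The data had been entered and checked when the SAP text was written. The documents do not say whether comparisons between products had been seen, so prespecification cannot be taken for granted.

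**Working it through.** **Inputs from the documents.** 30 participants (protocol, Study Protocol); sequences AB and BA, glucose at baseline and at 30, 60, 90 and 120 min (protocol, Data collection); trapezoidal iAUC above baseline, and Cmax as the highest value (SAP, Descriptive Statistic); p ≤ 0.05 per test (SAP, Bivariate and General Linear Model Analysis). Neither document gives an effect size, SD, correlation or power, so the plan has no error rate or power figure to reproduce.

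**Assumptions.** Tests are two-sided. No true effect. Success means that at least one of the listed tests is significant; the plan does not say this. The simulation used n = 30 (15 per sequence), two assumed glucose curves, AR(1) correlation of 0, 0.3, 0.6 or 0.9, and fasting/postprandial within-person SDs of 0.2/0.8, 0.4/1.0 or 0.8/1.2 mmol/L. That makes 2 × 4 × 3 = 24 scenarios, with 20,000 runs each. iAUC and Cmax were tested by paired t. The product effect and the product-by-time interaction were tested with the baseline difference as covariate. Age, ethnicity, gender and BMI were not simulated.

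**Reference values if tests were independent.**
- Two tests, two-sided: 1 − 0.95² = 9.75%. Three tests: 1 − 0.95³ = 14.3%.
- Favourable direction only, two tests: 1 − 0.975² = 4.9%. Three tests: 1 − 0.975³ = 7.3%.
- Favourable iAUC or Cmax, or any interaction: 1 − 0.975² × 0.95 = 9.7%.

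**Results.**

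| What counts as success | Simulated | If independent | One test |
|---|---|---|---|
| iAUC or Cmax, two-sided | 6.4–9.5% | 9.75% | 5% |
| iAUC, Cmax or interaction, two-sided | 10.7–14.2% | 14.3% | 5% |
| Favourable iAUC alone | 2.3–2.7% | – | 2.5% |
| Favourable iAUC or Cmax | 3.1–4.8% | 4.9% | 2.5% |
| Favourable iAUC, Cmax or product effect | 4.4–6.3% | 7.3% | 2.5% |
| Favourable iAUC or Cmax, or any interaction | 7.8–9.7% | 9.7% | 2.5% |

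As multiples, the two-sided three-test rule runs from 10.7/5 = 2.1 to 14.2/5 = 2.8. Favourable results on the directional measures run from 3.1/2.5 = 1.2 to 6.3/2.5 = 2.5, the upper end needing the implied product effect. Comparing the ends of the ranges, letting the undirected interaction count adds 7.8 − 3.1 = 4.7 to 9.7 − 4.8 = 4.9 percentage points, which is most of the excess under that rule.

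**Sensitivity.** With Wilcoxon in place of t, the three-test two-sided rate is 10.8–14.1%, favourable iAUC or Cmax 3.2–4.7%, and with the product effect 4.6–6.2%. Further simulations under separately chosen assumptions gave three-test rates within 10.7–14.0% and favourable iAUC-or-Cmax rates within 3.1–5.1%.

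**Disagreement under a true effect.** The postprandial rise was cut proportionally until iAUC had 78–83% power (5,000 runs per scenario). Exactly one of iAUC and Cmax was then significantly favourable in 8.8–38.9% of trials.

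**Check of a single primary test.** Regressing the within-person iAUC difference on the fasting difference and sequence gave 4.8–5.4% two-sided and 2.2–2.7% in the favourable direction, so the nominal level is kept.

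**The case against.** The strongest reply is that the objective is directional. A significantly worse iAUC or Cmax cannot show improvement, so the two-sided 10.7–14.2% counts results that nobody could claim as success. Read that way, the relevant figure for the two named summaries is 3.1–4.8% against 2.5%, which is real but modest. This stands as a matter of weight, and the directional figures should be read beside the two-sided one. It does not close the gap: the word *improved* gives no test and no rule, and the one ANCOVA effect that the SAP names has no direction.

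The inflation also depends on the assumed rule and correlations. If every test had to succeed, the error rate would not exceed 5%, though power would fall. With three tests at a common correlation of 0.9, the two-sided rate is 8.4%, so more than doubling is a feature of the simulated glucose structure and not a general law. The SAP also does not say how baseline enters the ANCOVA, so the simulated model is one reading of it. These limits stand.

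The disagreement range is wide and rests wholly on assumed effects and curves. Two endpoints differing is not itself an error; the range shows only that the missing rule could matter.

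Finally, naming one measure with its existing paired test would be enough, and a mixed model goes further than the defect requires. That is fair, and the model below is offered as an example. A registry record might name a primary outcome, but this point is confined to the two documents provided.

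**Conclusion.** The concern holds for these two documents. The plan lets its single primary claim rest on any of several unadjusted glucose tests, one of them undirected, and gives no means of judging the objective unmet. The inflation is conditional on an any-test-suffices reading, no true effect, n = 30, and assumed curves, SDs and correlations. On those terms it is about 2.1 to 2.8 times the nominal 5% two-sided for the three explicit tests, and about 1.2 to 2.5 times 2.5% when only favourable results on directional measures count. The absence of a primary test and success rule depends on none of those assumptions. This should be corrected.

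**What to change.** First, state whether product comparisons of glucose had been seen when the SAP was written.

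**If they had not,** name one directional glucose comparison as the single primary test at two-sided 0.05, and state that improvement is claimed only if that test is significant in the favourable direction. Make Cmax and all ANCOVA tests secondary. One suitable choice is 0–120 min iAUC in a linear mixed model with product and period as fixed effects, participant as random effect, and fasting glucose entered as the participant's two-visit mean plus that visit's deviation from it. With complete data this equals the regression of the iAUC difference on the fasting difference and sequence checked above. It is in line with the SAP's statement that "including baseline data as a covariate will improve the" analyses, although iAUC already subtracts baseline. Keeping a paired test for iAUC would also close the gap, provided the choice between t and Wilcoxon is fixed in advance.

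A single primary test is preferable to splitting alpha. With 30 pairs at two-sided 0.05, a paired t-test has 80% power for a standardised difference of 0.53. With Bonferroni over three tests (0.05/3 = 0.0167), power at that difference falls to 64%.

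**If they had,** report that no primary test was prespecified, and show all glucose tests together with estimates and 95% confidence intervals. No wording restores the 5% level in that case.

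**Cost.** A short SAP change and no new data. If the mixed model is chosen, its specification must be written out, because the SAP now assigns iAUC to a paired test without a covariate. A lone Cmax or interaction result could no longer carry the primary claim.

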Data collection

Participants attended the lab at 8 am with light clothing and were asked a series of questions to measure fasting, nutrition, physical activity and sleep regimen adherence. They were also required to hand in the completed questionnaire which consisted of dietary and physical activity information which were distributed to them before data collection. Then, height, weight, waist circumference, % body fat and blood pressure measurement were taken followed by a perceived satiety measurement and fasting capillary blood sample (baseline) withdrawal using the finger pricking method.

After that, the participants were randomized to consume one of the two types of test products namely A: control (glucose) and B: Formulation 3 (60% sweetener) dissolved in 180 mL plain water together with the standardized breakfast in treatment sequences (AB, BA). Each respondent consumed the meals in a separate place and avoided using electronic gadgets while eating to reduce distractions. They were instructed to consume the meals at a comfortable pace within 15 min. Participants were asked to remain rested in the same place during the testing period and allowed to read, use their phone or laptop and use the toilet after meals consumption. They have also refrained from excessive physical activity until the end of test visit.

At the first bite, a timer was started and postprandial blood samples as well as perceived satiety measurement were then taken at 30, 60, 90 and 120 min thereafter. Blood collection techniques adhered exactly as they were written in the standard operating procedure (SOP). After the 120 min assessments, participants were allowed to leave the testing site and instructed to record the food consumed for the rest of the day. The food record was aimed to explore the changes in food intake following each test food relative to usual food intake (baseline data) (Burton-Freeman et al., 2017). Also, they were given a new food log form and physical activity diary to fill in one day before the next study visit. Figure 3.4 displayed the study flow chart.

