eat, prospective food consumption and thirstiness) were calculated using the trapezoidal approximation (Winham et al., 2017). The maximum concentration (Cmax) of blood glucose levels were taken to be the highest concentration within the respective time interval (Stewart & Zimmer, 2017).

Nutritionist Pro was a dietary analysis software used for macronutrient and micronutrient analysis. This software consists of several food databases including the USDA Food Database, Canadian Food Database, Mexico Food Database and the Malaysian Food Composition Tables along with other hundreds of international food items. In this software, if the food item consumed by the participants was not available, the researchers can readily substitute it with other identical food items available in the databases. Besides, the standard recipe was created for food products that could not be found in any of the previously mentioned sources. The dietary intake of the participants for habitual, pre-test and test day were inserted in the software, and subsequently, the interested macronutrients (energy, carbohydrate, protein, fat, and dietary fibre) or micronutrients (calcium, magnesium, zinc, iron, selenium, Vitamin A, E, K, and C) were conveyed to SPSS for further analysis.

Bivariate and General Linear Model Analysis

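### The exploratory satiety AUC comparison makes no use of the fasting rating taken before each product; adjusting for it is cheap and would probably, though not certainly, gain precision

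*SAP*

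**What the plan says.** The Protocol describes the trial as "Open-label, randomised, placebo-controlled, crossover study with two intervention arms" and states that "The study was conducted in 30 participants". The primary objective is glycaemic; by contrast "the acute effect of MMT peel powder on perceived satiety and energy intake were explored".

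Under Data collection, body and blood-pressure measurements at the visit are "followed by a perceived satiety measurement and fasting capillary blood sample (baseline) withdrawal", all before the test product. Blood samples and "perceived satiety measurement were then taken at 30, 60, 90 and 120 min thereafter".

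The SAP (Descriptive Statistic) computes a two-hour area for glucose and for five appetite scales, the last named being "eat, prospective food consumption and thirstiness) were calculated using the trapezoidal approximation". The bracket that defines the area as incremental stands beside glucose and not beside satiety, so the natural reading is that the satiety area is total.

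Under Bivariate and General Linear Model Analysis, the outcomes for the paired t-test or Wilcoxon signed-rank test include "dietary intake, physical activity and perceived satiety (AUC"). The ratings themselves go to Friedman's test with Wilcoxon follow-up. The one model with covariates is the repeated measures ANCOVA of postprandial glucose. Straight after it the SAP remarks: "Rather than subtracting from baseline data alone, including baseline data as a covariate will improve" the performance of the analyses.

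**The concern.** Pairing removes stable differences between people. It does not remove the difference in one person's morning appetite between two visits. That difference is measured by the fasting rating, cannot be caused by the product, and enters the AUC twice: directly, as the first point of the trapezoid, and indirectly, to the extent that starting appetite persists into the later ratings. Left unadjusted, it stays in the residual variation of the product contrast.

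At stake is the width of the confidence interval for five appetite scales in 30 people. Satiety is in the trial's title, the data needed are already collected, and the SAP reports satiety data complete for all 30.

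**Working it through.** The documents give no power, SD or correlation for satiety, so there is no stated figure to reproduce.

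**Inputs from the documents.** n = 30, two-product crossover; ratings at 0, 30, 60, 90 and 120 min; significance level 0.05 (two-sided assumed).

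**1. Weight of the fasting rating.** The trapezoid weights are 15, 30, 30, 30, 15, which sum to 120. The fasting rating has weight 15/120 = 12.5%.

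**2. Effect of adjustment.** Let r be the correlation between the within-person fasting difference and the within-person AUC difference. Regress the second on the first and read the intercept as the product effect. Its expected variance relative to the paired t-test is

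ratio = (1 − r²)(1 + 1/(n − 3)) = (1 − r²)(1 + 1/27).

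The second factor is the cost of estimating the slope. Break-even is at r = √(1 − 27/28) = 0.19.

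For power, take a scale with 60% under the paired t-test (noncentrality 2.29, 29 df). Divide 2.29 by the square root of the ratio and use 28 df.

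| r (assumed) | variance ratio | power from 60% |
|---|---|---|
| 0 | 1.04 | 58% |
| 0.19 | 1.00 | 60% |
| 0.3 | 0.94 | 62% |
| 0.5 | 0.78 | 71% |
| 0.65 | 0.60 | 81% |

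In simulation (40,000 runs per setting, r from 0 to 0.6) type I error was 0.047 to 0.049 for both analyses.

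**3. Plausible r, equal SDs (assumed).** Suppose the within-person differences have equal SDs at all five times and a common correlation c between times. The squared weights sum to 3150, and 120² − 3150 = 11250, so

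r = (15 + 105c) / √(3150 + 11250c).

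- c = 0: 15/√3150 = 0.27, ratio 0.96
- c = 0.1: 25.5/√4275 = 0.39, ratio 0.88
- c = 0.2: 36/√5400 = 0.49, ratio 0.79
- c = 0.3: 46.5/√6525 = 0.58, ratio 0.69

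**4. Sensitivity: post-meal SDs twice the fasting SD (assumed).** Then r = (15 + 210c)/√(11925 + 38700c), which gives 0.14, 0.29, 0.41 and 0.51 at the same four values of c, with ratios 1.02, 0.95, 0.87 and 0.77.

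**5. Sensitivity: one shared visit effect (assumed).** Take a visit-level appetite SD of 6 to 12 rating units, rating error SD of 10 to 12, and carry-over of 25% to 100% into post-meal ratings. Then r is 0.38 to 0.78. Adding visit-level variation that arises only after the meal, with SD 6 or 12, lowers it to 0.28 to 0.72 or 0.18 to 0.60.

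**The case against.** **The planned test is sound.** In a randomised crossover the paired comparison of AUC is unbiased and holds its type I error. A reader might infer that a chance lean in fasting appetite towards one product biases the result. It does not: that is ordinary sampling variation, already counted in the paired test's standard error. This part of the objection stands in full.

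**The SAP does not contradict itself.** It is tempting to say the SAP endorses a baseline covariate and then ignores its own rule. But the sentence follows the glucose model and compares a covariate with subtracting the baseline. On the natural reading, nothing is subtracted from the satiety area. The sentence is not expressly confined to glucose, so carrying it over to satiety is a fair extension and no more. If the satiety area were meant to be incremental, the SAP's caution about subtraction would apply directly.

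**The gain may be small.** The Protocol (Pre-test protocol) standardises dinner, fasting, sleep, activity, caffeine and alcohol, partly so that appetite is alike at both visits. That limits the variation left to adjust for. The documents support no particular r, and below about 0.19 adjustment loses slightly. This stands, and is why the size is given as a range. The downside is bounded, however, at about 4% of variance.

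**The replacement is parametric, and late.** The plan keeps Wilcoxon for non-normal data, so a regression needs a fallback. The SAP also describes data checking as already done, so a change now may come after the results are known. Both points stand and are met in the fix.

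**Conclusion.** The point holds as an inexpensive improvement to an exploratory analysis. The documents establish that a fasting rating unaffected by the product is collected, makes up 12.5% of a total 0–120 min area, and is used by no satiety analysis as a covariate. They do not establish that precision is certainly lost, because r is unknown.

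Under equal SDs and between-time correlations of 0 to 0.3, r is 0.27 to 0.58 and the variance falls by about 4% to 31%. Under less favourable assumptions the result runs from a 4% loss at r = 0 to a moderate gain. Most of the range examined lies above break-even. All of this assumes a total area and refers to the paired t-test; the Wilcoxon version was not quantified.

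A reader might also want the same adjustment for test-day energy intake, using intake recorded the day before. The case for that is not made: an assumed r of 0 to 0.3 includes a net loss, so it is not recommended.

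**What to change.** In the SAP, Bivariate and General Linear Model Analysis:

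1. State that satiety AUC is the total area over 0–120 min.
2. For each scale, regress the within-person AUC difference (B minus A) on the within-person difference in that scale's fasting rating, with a centred sequence term to absorb the period effect. The intercept is the product effect at equal fasting appetite. An equivalent is a mixed model with product, period, the visit's fasting rating and the person's mean fasting rating.
3. Report the product effect with its 95% CI, and use a permutation or bootstrap version if residuals are clearly non-normal.
4. If product results have already been seen, keep the planned paired test, report the adjusted analysis beside it and label it as added later.

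The cost is SAP wording, one or two degrees of freedom per scale, and about 4% more variance (slightly more with the period term) if r is near 0. No new data are needed.

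### The time-course glucose model names only the treatment-by-time interaction as its test, so the baseline-adjusted analysis has no stated test of the overall product difference

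*SAP*

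**What the plan says.** The protocol describes a two-sequence crossover (AB, BA) and says "The study was conducted in 30 participants". Under Study Protocol, "the primary objective is to show an improved glycemic response"; no glucose measure is attached to that objective. Under Data collection, a fasting sample is drawn first, and the post-meal samples "were then taken at 30, 60, 90 and 120 min thereafter".

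The SAP, under Bivariate and General Linear Model Analysis, has two routes for glucose:

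- Paired t or Wilcoxon tests between products on iAUC and Cmax.
- A time-course model: "Two-way repeated measures ANCOVA was used to compare the postprandial blood glucose levels between two test products over different time points". The sentence continues "controlling for treatment and time to test for treatment by time interaction after adjustment for covariates", with age, ethnicity, gender and BMI in brackets.

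The SAP then argues that "including baseline data as a covariate will improve" the analyses compared with subtraction alone, and warns that subtracting baseline can produce artefacts. Baseline does not appear in the bracketed covariate list.

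**The concern.** The interaction asks whether the product difference changes across the time points. It does not ask whether there is a difference on average. If only post-meal points are in the time factor, a product that lowers all four by the same amount satisfies the interaction's null hypothesis exactly.

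Two misreadings of the results become possible. A real average reduction could be written up from this model as no significant effect. A pure change of shape, with no average reduction, could be written up as a success. The matter carries more weight because the SAP's own argument favours baseline adjustment over subtraction, and this model is the one meant to carry that adjustment. The software will probably print the main effect as well, but a printed result is not a pre-stated test.

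**Working it through.** The documents give no effect size, SD, correlation or power, so there is no planned figure to reproduce.

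**From the documents.** n = 30; products compared within person; post-meal times 30, 60, 90 and 120 min; significance level 0.05 (two-sided assumed).

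**Assumed.** The within-person product difference has SD 1 at each time, and differences at any two times, baseline included, have correlation ρ = 0.3, 0.5 or 0.7. The mean lowering over the four times is 0.5. Person-level covariates are left out at this stage.

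**Formulas.** Let d_j be the lowering at time j.

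- Product main effect: t test on the mean of the four differences, 29 df. SD of that mean = √((1+3ρ)/4) = 0.689, 0.791, 0.880. Noncentrality = 0.5·√30/SD = 3.97, 3.46, 3.11.
- Interaction: multivariate F on 3 and 27 df, noncentrality λ = 30·Σ(d_j − mean)²/(1−ρ).
 - Uniform (0.5 at each time): Σ = 0, so λ = 0 and power equals the significance level.
 - Mildly uneven (0.6, 0.6, 0.4, 0.4): Σ = 0.04, λ = 1.71, 2.40, 4.00.
 - Strongly early (0.9, 0.7, 0.3, 0.1): Σ = 0.40, λ = 17.1, 24.0, 40.0.
- Paired t test on net iAUC: trapezoidal weights −105 at baseline, then 30, 30, 30, 15. Mean = 105 × 0.5 = 52.5. The weights sum to zero, so variance = (1−ρ)·13,950 and SD = 98.8, 83.5, 64.7. Noncentrality = 52.5·√30/SD = 2.91, 3.44, 4.44.
- Main effect adjusted for the within-person difference in baseline: residual variance = (1+3ρ)/4 − ρ² = 0.385, 0.375, 0.285; SD = 0.620, 0.612, 0.534; 28 df.

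| Test | Lowering | ρ = 0.3 | ρ = 0.5 | ρ = 0.7 |
|---|---|---|---|---|
| Interaction, four post-meal levels | uniform | 5% | 5% | 5% |
| Interaction, four post-meal levels | mildly uneven | 15% | 20% | 31% |
| Interaction, four post-meal levels | strongly early | 91% | 98% | 100% |
| Main effect, unadjusted | any of these | 97% | 92% | 85% |
| Main effect, baseline-adjusted | any of these | 98–99% | 99% | 100% |
| Paired net iAUC | uniform | 80% | 91% | 99% |

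A simulation of 20,000 trials at ρ = 0.5, with a uniform lowering sized for 90% main-effect power, gave 5.1% for the interaction (univariate F test) and 89.8% for the main effect.

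**If baseline were a fifth time level.** With a uniform post-meal lowering the five differences are 0, 0.5, 0.5, 0.5, 0.5. Then Σ = 0.20, λ = 30·0.20/(1−ρ) = 8.6, 12, 20 on 4 and 26 df, and interaction power is about 55%, 72% and 92%.

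**Covariate centring.** In a repeated measures ANCOVA with person-level covariates entered uncentred, the product main effect is the difference at covariate value zero. Assuming age 35 (SD 10), BMI 27 (SD 4) and gender, simulation of the uniform case gives main-effect power of about 6–8% uncentred and about 85–97% centred.

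**The case against.** The strongest reply has four parts.

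- The sentence opens by stating a comparison between products, so the wording may be loose rather than wrong. That is possible, but the only effect it goes on to name as tested is the interaction.
- The four-level time factor is inferred. This stands as a caveat. The model is described as one of postprandial glucose, and a baseline used as a covariate is not also an outcome level, so four levels is the likelier reading. Still, baseline is missing from the bracketed list, and with five levels the interaction is far from powerless.
- The overall effect is tested elsewhere, by the paired tests on iAUC and Cmax. This largely stands for iAUC. The cover is partial because iAUC relies on the baseline subtraction that the SAP itself criticises, and in the uniform case it was never more powerful than the baseline-adjusted main effect at the correlations tried. Cmax addresses only the peak.
- A parallel shift is the worst case for the interaction, and nothing in the documents says it is expected. This stands: against a strongly early effect the interaction was more powerful than the unadjusted main effect at ρ = 0.5 and 0.7.

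A reader might infer that the plan has almost no power for its primary objective, or that a true reduction would be missed. The documents do not support either. The objective speaks of an improved response and could be met by a change in level, peak or shape, and iAUC would usually detect a uniform lowering of the size assumed.

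**Conclusion.** The point holds in a limited form. The SAP's baseline-adjusted time-course model names no test of the overall product difference, and the test it does name can be insensitive to one. The 5% figure under a uniform lowering follows from the algebra and needs only a time factor without baseline. The other figures depend on the assumed 0.5 SD mean lowering, the correlations and equal SDs, none of which the documents supply. The iAUC figures further assume that area below baseline is netted off. This is a weakness in the stated test that should be corrected. It does not invalidate the planned glucose analysis. Which of iAUC, Cmax or the time course answers the primary objective is a separate gap that this correction alone does not close.

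**What to change.** In the SAP, under Bivariate and General Linear Model Analysis:

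1. Name as the model's product test the mean product difference over 30–120 min, with a 95% CI.
2. Adjust it for each visit's own baseline, entered as a visit-level covariate or as the within-person baseline difference. A single baseline per person would not do this, because baseline differs between a participant's two visits.
3. Centre age, BMI and the other person-level covariates, so that the main effect is the average difference.
4. State that baseline is a covariate and not a level of time.
5. Keep treatment by time as a supportive description of shape.

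This needs no new data. It costs a few sentences of text and some care in setting up the model, and the interaction loses its place as the named test. The SAP's Data Checking and Normality Test section already reports 30 complete records, so the change should be dated and labelled as a late clarification, with the interaction result still reported.
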